Study protocol and statistical analysis plan

Study title Effect of Oral Estradiol and Progesterone Therapy on Vaginal Cytokines in Postmenopausal Women

NCT number NCT02224313

Date 08/04/2014

Participants

Twenty healthy women (10 premenopausal and 10 postmenopausal women) were asked to participate in this study. Premenopausal women were between the ages of 20-40 years, had regular menstrual cycles (regular menses during prior 3 months and had a luteal phase serum P4 >3ng/mL), and were not using any hormonal contraception. Postmenopausal women were between the ages of 45-65 years, amenorrhea for at least 12 months, had an intact uterus, were not on HT and had no contraindications to HT. All women were screened for genitourinary tract infections including bacterial vaginosis, chlamydia, gonorrhea and trichomoniasis and underwent a screening PAP smear. Women who did not have evidence of inflammation or infection based on vaginal wet preparations and PAP smears were included in the study. All participants provided a written Informed consent. The protocol was approved by the Eastern Virginia Medical School Institutional Review Board and registered on Clinicaltrial.gov NCT02224313 (August 25, 2014).

Study Design

Each woman was followed at three visits during one menstrual cycle in premenopausal women or during 28 days in postmenopausal women. For premenopausal women, visit 1 was during the follicular phase (days 7-10 of menstrual cycle), visit 2 was during ovulatory phase (days 12-16 of menstrual cycle), and visit 3 during luteal phase (days 19-23 of menstrual cycle). For postmenopausal women, visit 1 was at baseline (no hormones taken), visit 2 was after taking oral E2 1.0 mg daily for 14 days, and visit 3 was after taking oral E2 1.0 mg plus oral P4 100 mg daily for another 14 days. (Table 1)

At each visit, peripheral venous blood sample was obtained for estimation of serum E2 and P4 levels. A vaginal speculum examination was performed with a lateral vaginal wall swab for pH and vaginal epithelial cells for maturation index. A cervico-vaginal lavage using 5.0 mL of sterile saline was then carried out. The participants were instructed not to have intercourse for 48 hours prior to each examination and AbaCard p30 test confirmed the absence of semen in the vaginal canal at each visit.

Serum E2 and P4 analysis

Peripheral blood samples were allowed to clot at room temperature for 15 minutes, then centrifuged for 15 minutes at 4000 G. The resultant supernatant was aspirated into individual storage tubes and frozen until assayed for serum E2 and P4 level with a chemoluminescence technique.

Cervico-vaginal cytokine analysis

Cervico-vaginal lavage was performed by repetitive flushing of the lateral, anterior and posterior walls and fornices of the vagina with 5mL sterile saline using a 6-inch dropper. The resulting fluid sample was centrifuged for 10 minutes at 500 g to remove the cellular component

and debris, and the supernatant aspirated and stored in aliquots at -20°C for later testing. Cytokine levels of IL-8 and IL-1 β were measured in duplicate using cytokine specific sandwich ELISA kits (Millipore Sigma, Darmstadt, Germany). The individual wells were read at optical density 450 nm per manufacturer instructions and cytokine values in pg/mL were obtained by plotting along a standard curve of pure cytokine. As the IL-1 β concentrations fell below the lower limit of the kit detection, the samples were subsequently concentrated 4-fold with a centrifugal filter (Amicon Ultra-4 10K Centrifugal Filter Device from Millipore Sigma) and the ELISA assay for IL-1 β was repeated. The coefficients of variation for both IL-8 and IL-1 β are <10% for intra-assay and <12% for inter-assay, as determined by the manufacturer. Total protein concentration in the sample was determined with the bicinchoninic acid assay (Millipore Sigma). The levels of cervico-vaginal IL-8 and IL-1 β were normalized for the total protein concentration and presented as picogram per microgram of total protein (pg/ug protein).

Statistical analysis

Baseline descriptive statistics were reported as means \pm standard deviation for continuous variables and were compared between premenopausal and postmenopausal women with a student t-test. Mixed effects model for repeated measures compared serum E2, serum P4, cervico-vaginal IL-8 and IL-1 β levels between premenopausal and postmenopausal women for each visit. Changes of these levels across 3 visits were also explored within premenopausal and postmenopausal group. Pairwise comparison of measures between visits was predicted according to the mixed effects model presented as mean difference \pm standard error. Correlation between serum E2, serum P4 with cervico-vaginal IL-8 and IL-1 β levels was evaluated with Pearson's pairwise correlation stratified by premenopausal and postmenopausal group. The

correlation of changes in serum E2, serum P4 with changes in cervico-vaginal IL-8 and IL-1 β levels was also evaluated. All statistical tests were 2-sided and a p-value of 0.05 or less was considered statistically significant. The statistical analyses were performed in STATA software version 14.1 (StataCorp I.P. College station, Texas).

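### In postmenopausal women P4 is aliased with longer E2 exposure and time, and a P4-cytokine Pearson correlation pooled over visits can turn that aliasing into an apparent P4 association

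*Combined protocol and SAP*

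**What the plan says.** The Study Design section gives all postmenopausal women the same order of treatment. Visit 1 is before any hormone, and the second visit closes a fortnight on E2 alone. The final step of the sequence is worded as follows: "visit 3 was after taking oral E2 1.0 mg plus oral P4 100 mg daily for another 14 days". The section describes no reversed order, no E2-only continuation, no P4-only period and no untreated postmenopausal group. The premenopausal women take no study hormone and are seen in three phases of one natural cycle.

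The Statistical analysis section plans two analyses that bear on P4 in this group:

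- Visit contrasts: "Pairwise comparison of measures between visits was predicted according to the mixed effects model". Within-group changes across visits are described as explored.
- Association of serum E2 and serum P4 with each cytokine, by Pearson's "pairwise correlation stratified by premenopausal and postmenopausal group". Changes in hormones are also correlated with changes in cytokines.

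For the correlations the plan does not state which visits enter, how repeated values from one woman are handled, whether P4 is adjusted for E2, or over which interval changes are taken. All tests are two-sided at 0.05.

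**The concern.** Serum P4 should be low at visits 1 and 2 and raised at visit 3, because P4 is given only in the second fortnight. Pooled over visits, the P4 values then split mainly into visit 3 and not visit 3. A correlation of cytokine with P4 becomes close to a comparison of visit 3 with the mean of visits 1 and 2, expressed as a hormone association.

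That comparison also contains 14 further days of E2, 14 further days of time and a repeat lavage. If the cytokine is still drifting after day 14 for any of those reasons, the planned analysis can show a significant P4-cytokine correlation when P4 has no effect. Nothing in the plan separates the two explanations or warns the reader about them.

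**Working it through.** The plan gives no SD, effect size or power figure, so there is none to reproduce. The check has an algebraic part, which needs no assumed variances, and a numerical part, which is illustrative.

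**1. What the design can identify.** From the Study Design section, for a postmenopausal woman:

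| Visit | E2 on | P4 on | Days on E2 | Elapsed days |
|---|---|---|---|---|
| 1 | 0 | 0 | 0 | 0 |
| 2 | 1 | 0 | 14 | 14 |
| 3 | 1 | 1 | 28 | 28 |

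Days on E2 = 14 × (E2 on + P4 on) exactly, and elapsed days equal days on E2. With an intercept there are five terms and rank 3. Hence

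visit 3 − visit 2 = P4 effect + 14 × (daily E2-duration effect) + 14 × (daily time effect),

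and the P4 coefficient is not estimable.

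**2. Whether another group supplies the missing piece.**

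- Premenopausal women, with their own intercept and cycle-phase effects and shared visit effects: rank 6 of 9, P4 still not estimable. Their visits are tied to cycle phase.
- An untreated postmenopausal group alone: rank 4 of 5, P4 not estimable. It removes elapsed time, but P4 stays aliased with E2 duration.
- A postmenopausal group continuing E2 without P4: rank 4 of 5, P4 estimable, because the two groups' visit 3 − visit 2 differences differ only by P4.
- Both comparators: rank 5 of 5.

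**3. Expected pooled correlation when P4 does nothing.** Assumed, not from the documents: log-scale SD 0.8 between women and 0.5 within, and a fall of 0.5 in each 14 days. Take the limiting case in which P4 is a pure marker of visit 3.

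- Visit means 0, −0.5, −1.0. Visit 3 minus the mean of visits 1 and 2 = −1.0 − (−0.25) = −0.75.
- Marker variance = (1/3)(2/3) = 2/9, SD 0.471. Covariance = −0.75 × 2/9 = −0.167.
- Cytokine variance = 0.64 + 0.25 + 0.167 (variance of the visit means) = 1.057, SD 1.028.
- r = −0.167 / (0.471 × 1.028) ≈ −0.34.

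The critical |r| for 30 observations (28 df, t = 2.048) is 2.048/√(2.048² + 28) = 0.36, so a sizeable share of trials cross it.

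If the E2 effect is complete by day 14, the visit means are 0, −0.5, −0.5. The gap is −0.25, the covariance −0.056, the cytokine SD √(0.89 + 0.056) = 0.972, and r ≈ −0.12.

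**4. Simulated rejection rates, zero P4 effect.** Same SDs, 10 women, P4 about 0.3 ng/mL at visits 1–2 and 3 ng/mL at visit 3 (assumed):

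| Scenario and analysis | Significant |
|---|---|
| Fall of 0.5 per 14 days, pooled Pearson, log cytokine | about 27–40% |
| Same, untransformed cytokine | about 7–15% |
| Same, visit in the model | about 5% |
| E2 effect complete by day 14, pooled Pearson, log cytokine | about 2–4% |
| No drift at all, pooled Pearson, log cytokine | 0.4% |

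The ranges reflect the unknown spread of serum P4. The upper ends correspond to a P4 log-SD of 0.4; a wider spread gives lower rates.

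**5. A second set of assumptions.** With within-woman correlation 0.5, a tenfold P4 rise, and a non-P4 shift of 0, 0.5 or 1.0 SD at visit 3 only:

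- Pooled correlation significant in 1.1%, 16.6% and 67.7%.
- Correlation within visit 3, or of visit 2-to-3 changes: about 5% throughout.
- Change correlation pooling both intervals: 9.5%, 20.3% and 48.1%. The change analysis is therefore protected only if it is restricted to one interval.

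**The case against.** The strongest reply is that the plan states no P4-specific hypothesis. The title names estradiol and progesterone therapy jointly, within-group changes are only explored, and visit 3 is already described as E2 plus P4. A correlation is an association, not a causal claim. This stands for the visit contrast: a reader might infer that the plan intends visit 3 minus visit 2 as a P4 effect, but it does not say so. The reply is weaker for the correlation, which names serum P4 as the explanatory measure and carries no caveat.

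Second, the visit test itself is not faulty. Under falls of 0.25, 0.5 or 0.69 log units per 14 days it is significant in about 18%, 51% and 78% of simulated trials. A reader might take these for false-positive rates. They are power to detect a change that really occurs between the visits; only the attribution of that change is in doubt.

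Third, the correlation rates depend on the cytokine scale, the P4 spread and drift that continues after day 14. The plan mentions no log transformation, and the untransformed rates are lower. This stands, and it is why a range and the below-5% case are given. Nor does pooling inflate error by itself in these simulations: without drift the pooled test rejects less often than 5%.

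Fourth, stratification by menopausal group does not exclude separate correlations at each visit. If that was meant, a common drift would not create the association. The wording names no visit stratum, so pooling is the plain reading, but it is not certain.

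**Conclusion.** The concern holds in a limited form. The aliasing of P4 with longer E2 exposure and elapsed time is exact and rests only on the treatment sequence. The missing comparator is continued E2 without P4. It is tempting to say that the lack of an untreated group is the problem, but such a group alone would leave P4 aliased with E2 duration.

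The practical consequence falls on the P4-cytokine correlation in the postmenopausal group, if it is pooled over visits as the wording suggests. Its size is conditional on the assumed variances and P4 levels. It is substantial if the cytokine keeps changing after day 14, and absent if the E2 effect is complete by then. The documents do not show which case applies, nor that any spurious P4 claim was planned. This is a weakness in analysis specification and interpretation, not a calculation error, and it should be corrected.

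**What to change.** Leave the regimen and visits as they are and change the analysis text.

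1. In the postmenopausal group, replace the pooled Pearson correlation with a mixed model of each cytokine on serum P4 and serum E2, with woman as random effect and visit as fixed effect. Alternatively, report the correlation within visit 3, or of visit 2-to-3 changes.
2. State which visits enter each correlation and the interval over which changes are taken. Do not pool the two intervals. State the scale on which cytokines and hormones are analysed.
3. Label visit 3 minus visit 2 as the change over the second 14 days, with E2 continued and P4 added, and say that it is not an estimate of a P4 effect.

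The cost is some wording and one model term. The P4 association becomes less precise: within visit 3, 10 women (8 df, t = 2.306) need |r| above 2.306/√(2.306² + 8) = 0.63 for significance. It also remains observational, because it rests on differences in serum P4 between women on the same regimen. No analysis of these data recovers a P4-specific effect.

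### Does the plan need a direct between-group test of change across the three visits?

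*Combined protocol and SAP*

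**What the plan says.** All of this is in the Statistical analysis section unless another is named.

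- A repeated-measures mixed model compares serum E2, serum P4, IL-8 and IL-1β "between premenopausal and postmenopausal women for each visit". This is a comparison of levels.
- Change is handled inside each group: "Changes of these levels across 3 visits were also explored within premenopausal and postmenopausal group".
- Visit contrasts come from the same model: "Pairwise comparison of measures between visits was predicted according to the mixed effects model". They are to be shown as mean differences with standard errors.
- The only decision rule is general: "All statistical tests were 2-sided and a p-value of 0.05 or less was considered statistically significant".
- Changes in hormones are correlated with changes in cytokines. That does not compare the groups.

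The Participants section gives the size: "Twenty healthy women (10 premenopausal and 10 postmenopausal women) were asked to participate in this study". Study Design gives the layout: "Each woman was followed at three visits during one menstrual cycle in premenopausal women or during 28 days in postmenopausal women". The fixed effects of the model are not listed, and no group-by-visit interaction or difference in change is named.

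**The concern.** Two groups seen at three visits invite the question whether their courses differ, or whether postmenopausal women move towards premenopausal levels on therapy. The outputs named do not answer that directly. A reader could be tempted by two shortcuts: a significant change in one group but not in the other, or a significant group difference at visit 1 that is no longer significant at visit 3. Neither tests a difference in change. With 10 women per group, either pattern can arise by chance when the true changes are equal. A non-significant difference at one visit would also be too imprecise to show that levels are equal. At stake would be a mistaken statement about differential change.

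**Working it through.** The documents give no SD, effect size or power calculation, so there is no stated figure to reproduce. From the documents: n = 10 per group, three visits, two-sided 0.05. Assumed: normal data, equal SDs, no missing visits, within-woman correlation ρ from 0.3 to 0.7, and the effect sizes below.

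**1. Is the contrast already within the model?** Let D(v) be the postmenopausal minus premenopausal mean at visit v, and C(g,v) the change from visit 1 to visit v in group g. Then

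C(post,v) − C(pre,v) = D(v) − D(1).

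In a model without group-by-visit terms D(v) is the same at every visit, and a separate comparison at each visit would have no meaning. One joint model that gives the planned outputs therefore carries these terms. If the visit differences are shown by group, the two groups are different women, so the contrast is one subtraction with SE ≈ √(SE_post² + SE_pre²).

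**2. How misleading are the shortcuts?** Suppose both groups have the same true change d, in SDs of change. With p the one-sample t-test power (n = 10, 9 df), the chance that exactly one group is significant is 2p(1 − p). The last column repeats this for a compound-symmetry mixed model with a shared residual on 36 df, which is closer to the planned analysis.

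| d | p (9 df) | 2p(1 − p) | Mixed model, 36 df |
|---|---|---|---|
| 0 | 0.050 | 9.5% | 9% |
| 0.5 | 0.293 | 41% | 43% |
| 0.7 | 0.506 | 50% | 47% |
| 0.9 | 0.717 | 41% | 32% |
| 1.2 | 0.920 | 15% | 8% |
| 1.5 | 0.987 | 2.5% | 0.8% |

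Now suppose the gap between groups is constant, in SDs of level. The simulated chance of significance at visit 1 but not at visit 3 (t-tests, 400,000 runs per cell) is:

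| Gap | ρ = 0.3 | ρ = 0.5 | ρ = 0.7 |
|---|---|---|---|
| 0 | 4.6% | 4.2% | 3.4% |
| 0.6 | 15.7% | 13.3% | 10.3% |
| 0.9 | 20.5% | 17.2% | 13.1% |
| 1.5 | 8.9% | 7.6% | 6.0% |
| 2.0 | 1.1% | 1.0% | 0.9% |

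A direct contrast of change rejects in 4.9% to 5.1% of runs in every cell. The 95% half-width of a difference at one visit is t(0.975, 18) × √(2/10) = 2.101 × 0.447 = 0.94 SD.

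**3. What would naming the contrast add?** For a difference in change δ, in SDs of change, the test has 18 df and noncentrality δ/√(2/10).

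- δ = 0.5: noncentrality 1.12, power 18.5%.
- δ = 1.0: noncentrality 2.24, power 56%.
- 80% power needs δ ≈ 1.32. Multiplied by √(2(1 − ρ)), this is 1.57, 1.32 and 1.03 SDs of level for ρ = 0.3, 0.5 and 0.7.
- Two contrasts for each of four outcomes make eight tests. If they were independent, the chance of at least one false positive is 1 − 0.95⁸ = 34%.

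**4. What would it mean?** In Study Design the premenopausal visits are follicular, ovulatory and luteal phases. The postmenopausal visits are no hormone, E2, and E2 plus P4. The groups are not randomised and differ in age (20–40 against 45–65). A difference in change sets a cycle-phase shift against a treatment-stage shift, so it does not estimate a treatment effect. Four of the eight tests concern serum E2 and P4, the hormones that the postmenopausal women are given.

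**The case for a change.** The best case for a change is that it costs no new data and closes a real gap. The fixed effects are not listed, so separate models for each group cannot be ruled out. A contrast that can be estimated but is not named is also not committed to. The design invites the question, and the only stated criterion is a p-value threshold applied test by test. Low power is a reason to give an estimate with an interval, not a reason to leave it out. The lack of randomisation limits the planned per-visit comparisons just as much.

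Much of this stands. The text does omit the contrast, and the shortcuts are poor evidence at moderate effects. But the argument needs a claim that the documents do not make. They state no aim about differential change, narrowing or equality. Nor would a reader have only p-values to go on, because mean differences with standard errors are planned. The text does not say outright that these are given by group, but they follow directly on the sentence about within-group change. Separate models are possible, yet a single model is the more natural reading of the section.

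**Conclusion.** No change to the plan is called for. Followed as written, it gives valid per-visit group differences and within-group changes, and the changes in the postmenopausal group address the question in the title. The unlisted group-by-visit terms are a detail that the planned outputs imply. The unnamed contrast is an optional extra of low precision (80% power only at about 1.32 SD of change) and limited meaning in this design. Leaving it out of a small study that describes its analysis of change as exploratory is a fair choice.

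The error rates for the shortcuts, up to about 50% and 20%, apply only if someone draws that inference, and only at moderate effects. They rest on assumed effect sizes and correlations. The separate t-tests also overstate the first of them at larger effects: 41% against 32% at d = 0.9, and 15% against 8% at 1.2. What remains is a caution for reading the results: a statement about differential change should rest on the difference in change with its interval, and a non-significant difference at one visit does not show equality. The conclusion assumes one joint model and no claim of differential change. It would need another look if the sponsor meant to make such a claim.
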